6.14.1.3 Weiss Functional Impairment Rating Scale – Parent Version (WFIRS-P)

WFIRS-P comprises 50 items grouped into six domains: Family, School (learning and behavior), Life Skills, Child's Self-Concept, Social Activities, and Risky Activities. The items relate to the past month and are scored using a 4-point (0, 1, 2 and 3) Likert scale. Higher WFIRS-P scores indicate more severe functional impairment. Missing items do not include omitted responses in the scoring (i.e., treat as "not applicable"). Each of the six domains is scored omitting items with a missing or 'not applicable' response. The WFIRS-P average score will be calculated over the 50 items as sum of all items with a response divided by total number of items that have been endorsed (e.g., do not include 'not applicable' items in the total). The same approach will be used for the subscores. The change from baseline in WFIRS-P to Week 8 (EOS) will be analyzed using ANCOVA model with fixed effects for treatment and baseline as a covariate. Missing Subscale scores and Total Score will be handled using multiple imputation under MAR assumption for inferential analyses. Each of the treatment groups (SPN-812 ER 200 mg and 400 mg) will be compared with the Placebo. The p-values, LS means of treatment groups, differences between the LS means and placebo, and 95% confidence intervals for the treatment differences will be computed. The summary of this analysis will be presented in Table 14.2.2.1.3 and Listings 16.2.6.9, 16.2.6.10 and 16.2.6.11.

6.14.2 Analysis of Additional Secondary endpoints

6.14.2.1 Responder Analysis (50% responder rate)

For each subject, the response indicator variable will be set equal to 'YES' if a subject's % reduction $\geq 50\%$ or 'NO' otherwise. Percent reduction will be calculated as: % reduction = $100 * (\text{ADHD-RS-5 Total Score at Week 8 (EOS)} - \text{Baseline ADHD-RS-5 Total Score}) / \text{Baseline ADHD-RS-5 Total Score}$. The proportion of responders will be presented for each treatment group. The 2-sided 95% CI around the difference in proportions (SPN-812 200 mg ER minus Placebo, SPN-812 400 mg ER minus Placebo) and the p-value from Pearson's Chi-squared Test or Fisher's Exact Test will be presented. The summary of this analysis will be presented in Table 14.2.2.2.1.

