2.2 Secondary Objectives

2.2.1 Key Secondary Objectives:

To assess the effect of SPN-812 ER as assessed by:

1. Clinical Global Impression-Improvement (CGI-I)
2. Conners 3rd edition (Conners 3) – parent
3. Weiss Functional Impairment Rating Scale – Parent report (WFIRS-P)

2.2.2 Additional Secondary Objectives:

1. 50% Responder rate in ADHD-RS-5 Total score
2. Parenting Stress Index, Fourth Edition, Short Form (PSI-4-SF)
3. ADHD-RS-5 Inattention/Hyperactivity/Impulsivity subscale scores

4. Conners 3rd edition (Conners 3) – self, composite T-score (ages 8-11)

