3.5 Sample Size and Power Considerations

Seventy-two subjects per treatment group in the ITT population will yield 90% power at a significance level of 0.05 (two-sided) using a two-sample t-test with equal allocation to the treatment

groups. This assumes an effect size of 0.547, observed in the comparison of SPN-812 200 mg and placebo in the SPN-812 Phase IIb study (based on the CFB to endpoint in the ADHD-RS-IV total score). A total of 300 subjects (100 subjects in each of the three treatment groups) will be randomized to account for an anticipated 27.9% of randomized subjects not completing the study.

4 Definitions and Derivations

1. Baseline: Unless specified otherwise, baseline is defined as the non-missing value collected most recent to and before the time of the very first dose of the SM.
2. The study day (DY) is calculated as Visit date minus Reference date + 1 day if the visit date occurs on or after the reference date or Visit date minus Reference date if the visit date occurs before the Reference date, where the Reference date is defined as the first dose date (DY=1)
3. The change from baseline at a given Visit = observed value at that Visit minus observed value at baseline
4. ADHD-RS-5 total score =sum of scores for the 18 behaviors
5. ADHD-RS-5 Inattention subscale score = sum of scores for the first 9 behaviors
6. ADHD-RS-5 Hyperactivity/Impulsivity Subscale score = sum of scores for the last 9 behaviors
7. Conners 3-Parent Reported score: Composite T-score calculated by averaging over the 6 domains
8. Conners 3-Parent Reported score: T-score for individual domain: inattention, hyperactivity/impulsivity, aggression, executive functioning, learning problems, and relationships
9. Conners 3-Self Reported score domains: Composite T-score over the 5 domains
10. Conners 3-Self Reported score domains: inattention, hyperactivity/impulsivity, aggression, learning problems, and relationships
11. WFIRS-P score=average of all 50 items
12. WFIRS-P subscale scores: average of items of following 6 subdomains: Family, School (learning and behavior), Life Skills, Child's Self-Concept, Social Activities, and Risky Activities
13. PSI-4-SF: score=sum of all 36 items
14. PSI-4-SF: subscale scores: sum of items of following 3 subdomains: parental distress (PD), parent-child dysfunctional interaction (P-CDI), and difficult child (DC)

5 Study Variables

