5.1 Primary Efficacy Variable

The ADHD-RS-5 is an ADHD-specific rating scale designed and validated to assess current ADHD symptomatology as described in the fifth edition of the Diagnostic and Statistical Manual of Mental Disorders (DSM-V). The scale consists of 18 items that directly correspond to the 18 DSM-V symptoms and are further subdivided into two subscales: Hyperactivity/Impulsivity and Inattentiveness ([DuPaul, 2016](#)). The ADHD-RS-5 scale rates the frequency and severity of each symptom on a 4-point Likert-type scale from 0 (none) to 3 (severe) and allows assessment of functional impairments linked to each symptom dimension. The ADHD-RS-5 rating scale is one of the most commonly used measures of drug efficacy in the treatment of ADHD and is the primary outcome measure for this study. The ADHD-RS-5 Home Version: Child instrument will be administered and scored by Investigator at each weekly visit from Baseline through EOS.

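### The 50% responder formula in SAP Section 6.14.2.1 has its sign reversed: it counts subjects who worsen by at least half and codes every true responder as NO

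*SAP*

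**What the plan says.** The 50% responder rate is listed among the additional secondary objectives in SAP Section 2.2.2 ("50% Responder rate in ADHD-RS-5 Total score"). Section 6.14.2.1 sets the rule: "the response indicator variable will be set equal to 'YES' if a subject's % reduction $\geq 50\%$ or 'NO' otherwise". It then defines the quantity being compared with 50: "Percent reduction will be calculated as: % reduction = $100 * (\text{ADHD-RS-5 Total Score at Week 8 (EOS)} - \text{Baseline ADHD-RS-5 Total Score", with the baseline score as denominator.

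The direction of the scale is fixed elsewhere. Section 5.1 states that the instrument "rates the frequency and severity of each symptom on a 4-point Likert-type scale from 0 (none) to 3 (severe"), and Section 4 defines the total: "ADHD-RS-5 total score =sum of scores for the 18 behaviors". Section 4 also gives the general convention for change: "The change from baseline at a given Visit = observed value at that Visit minus observed value at baseline". That convention is correct for change from baseline and needs no amendment. It matters here only because the responder formula has the same sign.

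**The concern.** The label and the formula contradict each other. A reduction should be positive when the score falls, but the expression given is negative when the score falls. Combined with a threshold of +50 or more, the rule selects subjects whose symptoms increased by half or more.

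Applied literally, the table of responders would show the proportion who deteriorated markedly. Section 6.14.2.1 takes differences as active minus placebo, so a positive difference, which a reader would take as benefit, would mean more marked worsening on active treatment.

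Section 1 says the SAP supersedes the statistical methods in the protocol, so a correct formula there, if one exists, would not formally override this one. Section 1 also requires departures from the SAP to be identified and justified in the study report. Leaving the formula alone therefore means either reporting an inverted endpoint or departing from a pre-specified derivation, possibly after unblinding.

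**Working it through.** Section 6.14.2.1 states no numerical result, so there is no figure of the plan's own to reproduce. The check evaluates the written rule against the rule its label describes.

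**Inputs**
- Items scored 0 (none) to 3 (severe): Section 5.1.
- Total is the sum of 18 items: Section 4. Range 0 to 18 × 3 = 54; higher is worse.
- Responder if the value is at least 50: Section 6.14.2.1.
- Written formula: W = 100 × (Week 8 − Baseline)/Baseline.
- Formula matching the label: R = 100 × (Baseline − Week 8)/Baseline = −W.

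**Sign.** If Week 8 is below baseline, W is negative. Its lowest possible value, at a Week 8 score of 0, is −100. No subject who improves can reach +50.

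**Examples**

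| Baseline | Week 8 | W (as written) | Coded | R (as labelled) | Coded |
|---|---|---|---|---|---|
| 44 | 20 | 100 × (20 − 44)/44 = −54.5 | NO | +54.5 | YES |
| 40 | 20 | −50 | NO | +50 | YES |
| 40 | 0 | −100 | NO | +100 | YES |
| 40 | 40 | 0 | NO | 0 | NO |
| 40 | 54 | +35 | NO | −35 | NO |
| 36 | 54 | +50 | YES | −50 | NO |
| 30 | 45 | 100 × (45 − 30)/30 = +50 | YES | −50 | NO |

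**Ceiling.** W ≥ 50 requires Week 8 ≥ 1.5 × Baseline. With a maximum of 54, Baseline ≤ 54/1.5 = 36. A subject with a baseline above 36 cannot be coded YES whatever happens. Section 6.14 truncates imputed values to the range of the scale, so imputation does not lift this ceiling.

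**Full grid.** Take every whole-number baseline from 1 to 54 and every Week 8 score from 0 to 54:
- possible pairs: 54 × 55 = 2,970;
- true reductions of at least 50% (R ≥ 50): 783;
- flagged YES by the written rule (W ≥ 50): 972, all increases of at least 50%;
- pairs in both sets: 0.

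These counts describe possible scores and are not expected frequencies. They show a complete inversion, with no overlap between the two rules.

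**Anything that reverses the sign elsewhere.** No other section of the SAP gives a second responder formula, takes an absolute value, or sets the threshold at −50 or below.

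**The case against.** The strongest reply is that the intent is plain. The section heading, the term used for the quantity, the positive threshold and the objective in Section 2.2.2 all point to a fall of at least half. A programmer reading the whole section would probably notice, and implausible responder rates would probably be caught when the tables were reviewed. This is fair, and it means misreporting is a risk and not a certainty. It does not make the formula right: an SAP is meant to fix derivations before database lock, and this one fixes the wrong derivation.

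The second reply concerns quality control. Section 7 has all derived datasets independently programmed, but from the analysis data specifications, which are not part of the SAP. Whether they carry the reversed sign is unknown. If they do, two programmers would agree on the wrong variable, because double programming tests agreement with the specification and not the specification itself. If they do not, the datasets would contradict the SAP.

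The third reply is that literal use need not give rates near zero in every arm. This stands. The SAP gives no baseline distribution, so only the cut-off at 36 is certain. Likewise, the direction of any difference between arms depends on how treatment affects marked worsening.

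The fourth reply is that the endpoint has limited weight. Section 6.13 confines multiplicity adjustment to the primary and key secondary endpoints, and the sequence in Section 6.14.1 does not include the responder rate. This also stands, and it limits the reach of the error.

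**Conclusion.** The error holds as stated. As written, every subject with a true reduction of 50% or more is coded NO, and only subjects who worsen by 50% or more, necessarily from a baseline of 36 or below, are coded YES. This rests on nothing beyond the SAP's own formula, threshold and scale definition.

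It should be corrected before database lock, because the stated derivation produces the opposite of the named endpoint. The primary MMRM, the placebo-based sensitivity analysis, the key secondary testing sequence and the sample size do not use this variable and are not affected.

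**What to change.** In Section 6.14.2.1, define % reduction = 100 × (Baseline ADHD-RS-5 total − Week 8 (EOS) ADHD-RS-5 total)/Baseline ADHD-RS-5 total and keep the threshold of at least 50%. Equivalently, keep the present expression, rename it percent change, and code YES when it is −50% or lower.

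Check that the analysis dataset specification carries the same formula and threshold. A test case such as 44 to 20 (YES) and 30 to 45 (NO) would confirm the direction. Section 4 needs no change.

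This is a one-line correction to the SAP and, if needed, to the specification. It has no effect on trial conduct, sample size or blinding.

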6.14.1.1 Clinical Global Impression – Improvement (CGI-I)

The absolute value of CGI-I at week 8(EOS) will be analyzed using ANCOVA with treatment as a fixed classification variable and baseline CGI-S as a covariate. This ANCOVA analysis supersedes the ANOVA analysis described in the protocol. Each of the treatment groups (SPN-812 ER 200 mg and 400 mg) will be compared with the Placebo. The p-values, Least Squares means of the treatment groups, differences between the LS treatment means and placebo (SPN-812 ER 200 mg minus Placebo and SPN-812 ER 400 mg minus Placebo), 95% confidence intervals for the treatment differences will be computed. The summary of this analysis will be presented in Table 14.2.2.1.1 and listed in Listings 16.2.6.3.2- 16.2.6.5.

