6.14.2.3 ADHD-RS-5 Hyperactivity/Impulsivity and Inattention Subscales

The change from baseline to EOS in ADHD-RS-5 Inattention and the change from baseline to Week 8 (EOS) in Hyperactivity/Impulsivity subscales will be analyzed using ANCOVA model with fixed effects for treatment, age group and baseline as a covariate. Each of the treatment groups (SPN-812 ER 200 mg and 400 mg) will be compared with the Placebo. The p-values, LS means of treatment groups, differences between the LS means and placebo will be presented. The summary of this analysis will be presented in Table 14.2.2.3.

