6.14.2.5 Categorical Analysis of CGI-I

Categorical analysis will be performed using Pearson's Chi-square test by dichotomizing the CGI-I score as 'Improved' if the score is 'very much improved' or 'much improved' and 'Not Improved', otherwise, and will be presented for each visit in Table 14.2.2.5.

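### The 50% ADHD-RS-5 responder rate and the dichotomised CGI-I are compared without baseline adjustment, unlike the continuous analyses of the same scales: a minor efficiency and consistency point

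*SAP*

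**What the plan says.** **Binary analyses.**
- SAP 6.14.2.1 classes each subject as a 50% responder or not on ADHD-RS-5 total score. It gives a 95% CI for the difference in proportions for each dose against placebo, and "the p-value from Pearson's Chi-squared Test or Fisher's Exact Test will be presented". No covariate is named.
- SAP 6.14.2.5 uses Pearson's "Chi-square test by dichotomizing the CGI-I score" and reports it for each visit. It names no covariate, effect estimate or interval. Fisher's test is not mentioned there, but the general rule in 6.1 allows exact methods when expected counts are small.

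**Continuous analyses of the same scales.**
- The primary MMRM (6.13.1) includes baseline ADHD-RS-5 total score and age group.
- The ADHD-RS-5 subscale models (6.14.2.3) have "fixed effects for treatment, age group and baseline as a covariate".
- CGI-I as a score (6.14.1.1) is analysed by "ANCOVA with treatment as a fixed classification variable and baseline CGI-S as a covariate". The SAP says that this replaces the protocol's ANOVA.

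**Context.** Table 1 schedules ADHD-RS-5 and CGI-S at Visit 2, and 6.7 lists age group as a baseline variable. Section 6.13 limits multiplicity control to the primary and key secondary endpoints; both binary analyses are additional secondary. Section 6.14 puts all secondary analyses on the ITT population with missing Week 8 values imputed 100 times.

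**The concern.** The SAP moved the CGI-I score from an unadjusted to a baseline-adjusted analysis, then left baseline out when the same score is dichotomised. ADHD-RS-5 total score and its responder version differ in the same way.

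If baseline predicts the binary outcome, an unadjusted comparison has a wider interval and lower power than the collected data allow. A chance imbalance at baseline would also be corrected in the continuous result but not in the binary one, so the two could diverge partly for that reason. What is at stake is some precision, and agreement between paired results on one scale. The primary and key secondary conclusions are not affected.

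**Working it through.** **1. The plan's own figure (SAP 3.5).** The plan needs 72 per arm in ITT for 90% power by a t-test at two-sided 0.05. On the effect it says: "This assumes an effect size of 0.547, observed in the comparison of SPN-812 200 mg and placebo".
- Normal formula: n = 2(1.960 + 1.282)² / 0.547² = 70.2, so 71 per arm. The t-test version gives 71.2, so 72. Power at 72 is 90.3% (t-test).
- Dropout: 72 / (1 − 0.279) = 99.9, so 100 per arm.

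The figure reproduces. It concerns the continuous primary endpoint and does not depend on the binary tests.

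**2. General size of the effect.** Let R² be the within-arm share of the binary outcome's variance that baseline explains. The SE shrinks by about √(1 − R²), which is the same as an effective n of n/(1 − R²). The SAP gives neither response rates nor R², so both are assumed. With 20% vs 40% and 72 per arm:
- Null SE = √(2 × 0.3 × 0.7 / 72) = 0.0764; alternative SE = √((0.16 + 0.24) / 72) = 0.0745.
- Crude power = Φ[(0.20 − 1.96 × 0.0764) / 0.0745] = 75.0%.

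| R² (binary) | SE ratio | Power, 72 per arm |
|---|---|---|
| 0 | 1.000 | 75.0% |
| 0.02 | 0.990 | 75.9% |
| 0.05 | 0.975 | 77.2% |
| 0.10 | 0.949 | 79.4% |

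**3. The responder endpoint itself.** Percent reduction divides by baseline, so R² cannot be chosen freely and the endpoint was simulated. Assumptions: baseline mean 44, SD 6.5; Week 8 SD 13, placebo mean 32; effect 0.547 SD; scores held within the scale; response read as a fall of at least 50% from baseline (the formula as printed has the opposite sign, a separate matter). There were 4,000 trials per setting. The crude two-proportion test was compared with a baseline-adjusted risk difference with robust SE.

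| Baseline–Week 8 correlation | R² (72 per arm) | 72 per arm: crude / adjusted | 100 per arm: crude / adjusted |
|---|---|---|---|
| 0.2 | 0.002 | 71.9 / 72.2% | 85.2 / 85.1% |
| 0.3 | 0.001 | 74.9 / 75.2% | 87.1 / 86.8% |
| 0.4 | 0.013 | 76.1 / 76.7% | 89.6 / 89.8% |
| 0.5 | 0.038 | 78.4 / 80.2% | 89.9 / 91.1% |
| 0.6 | 0.081 | 81.6 / 84.5% | 92.1 / 93.9% |

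The pattern has a simple reason. Response means that the Week 8 score is at most half of baseline. The slope of Week 8 on baseline is the correlation × 13/6.5, or twice the correlation. When that slope equals 0.5 (correlation 0.25), baseline says almost nothing about response. Only well above that does adjustment gain anything.

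**4. CGI-I 'Improved'.** CGI-I is not divided by a baseline value, so a generic latent-variable simulation is used: 100 per arm, assumed rates 25% vs 42%, 12,000 trials per setting, crude chi-square vs logistic-standardised risk difference.

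| Latent variance explained | Power, crude / adjusted | Raw gain | Gain less 0.6 |
|---|---|---|---|
| 5% | 72.5 / 74.1% | 1.6 | 1.0 |
| 10% | 72.5 / 75.5% | 3.0 | 2.4 |
| 20% | 73.0 / 78.3% | 5.3 | 4.7 |

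The last column removes a part of the gain that is not due to adjustment. The chi-square test pools the variance and the standardised difference does not. Exact enumeration at 100 per arm and 25% vs 42%, with no covariate, gives 72.8% for the chi-square and 73.4% for an unpooled Wald test, a difference of 0.6 points. Under no effect (30% in both arms, 10% of latent variance explained), simulated type I error was 4.7% crude and 4.9% adjusted.

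**The case against.** Pearson and Fisher tests are valid for a randomised comparison, and both sections follow the SAP's own rule for categorical data in 6.1, so nothing is contradicted. Baseline-adjusted inference on both scales is already planned where it counts: the MMRM for ADHD-RS-5 and the key secondary ANCOVA for CGI-I. The binary versions carry no error-controlled claim. Dichotomising can itself make the continuous and binary results disagree. All of this stands, and it keeps the point minor.

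A reader might infer that the crude tests are biased, or that they certainly lose precision. The documents do not support either: type I error is held, and the loss depends on a baseline–outcome association that the SAP does not report. A reader might also apply the largest simulated gain (73% to 78%) to the responder rate. That figure comes from a generic covariate explaining 20% of latent variance, which nothing in the SAP supports, and it ignores that percent reduction already contains baseline.

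The objection does not remove the inconsistency. The plan adjusts the score and not its dichotomy, with the covariate already in hand.

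**Conclusion.** The point holds as a minor efficiency and consistency matter on two additional secondary analyses. The crude tests are valid, and neither the sample size nor the controlled endpoints are touched.

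For the responder rate, the change in power is about zero at correlations of 0.2 to 0.4 and about 1 to 3 points at 0.5 to 0.6. For CGI-I 'Improved' it is roughly 1 to 2 points if baseline CGI-S explains 5 to 10% of latent variance. All of these sizes rest on assumed response rates, variances and associations. The case for changing the plan is that the covariates are free and the two analyses of each scale would then match, rather than that much power is being lost.

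**What to change.** For each dose against placebo, make the main binary result a covariate-standardised difference in proportions, with 95% CI and p-value, from a logistic model with the covariates of the matching continuous analysis:
- **Responder rate:** treatment, baseline ADHD-RS-5 total score and age group, as in 6.13.1.
- **CGI-I 'Improved', at each visit:** treatment and baseline CGI-S, as in 6.14.1.1. Age group should not be added, because the CGI-I ANCOVA does not have it.

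At Week 8, pool the estimates and SEs over the 100 imputations with PROC MIANALYZE, which 6.13.2 already uses. This also supplies a combining rule, which 6.14.2.1 does not state for its p-value, and gives CGI-I 'Improved' an effect estimate and interval. Keep the crude proportions and the chi-square or exact test as supportive.

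The cost is SAP wording and a little more programming, including the standardisation and pooling steps, and a p-value that depends on a model. The risk-difference scale is kept.

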6.14.2.2 Short form of the PSI-4 (PSI-4-SF)

PSI-4-SF consists of 36 items divided into three domains: parental distress, parent-child dysfunctional interaction, and difficult child, which is scored using a 5-point as 1 (Strongly disagree), 2 (Disagree), 3 (Not sure), 4 (Agree), 5 (Strongly agree). For Item-32, the subject's original response

categories from the Answer Sheet are rated as 1 = “much harder than I expected” to 5 = “much easier than I expected”. This will be reversed prior to calculating the subscale and total domain scores. The reversed Item-32 will be scored as from 5 = “much harder than I expected” to 1 = “much easier than I expected”.

Scores will be calculated if:

1. No more than 1 item is missing from any subscale

If the above criteria are met, then the missing data convention is:

1. Identify the domain from which the item response is missing
2. Compute the average raw score for the completed items within that subscale, and round the average to the nearest whole number.
3. Assign the rounded whole number score to the missing item and then the subscale score

Domains and Subscales:

1. Sum responses items 1-12 = **PD** - Parental Distress
2. Sum responses items 13-24 = **P-CDI** - Parental-Child Dysfunctional Interaction
3. Sum responses items 25-36 = **DC** - Difficult Child

Total Stress Score (TS) = PD + P-CDI + DC

The change from baseline in PSI-4 total score to Week 8 (EOS) will be analyzed using ANCOVA model with fixed effects for treatment and baseline as a covariate. Each of the treatment groups (SPN-812 ER 200 mg and 400 mg) will be compared with the Placebo. The p-values, LS means of treatment groups, differences between the LS means and placebo will be presented. The summary of this analysis will be presented in Table 14.2.2.2 and Listings 16.2.6.12 - 16.2.6.14.

